7.3.2 Secondary endpoint analyses

Time to event endpoints will be analysed using Cox proportional hazard model as described for the primary endpoint analysis. All change from baseline endpoints specified in [Section 5.1.2](#) will be analysed using the restricted maximum likelihood (REML) based mixed effects model with repeated measurements (MMRM). The model will include the fixed, categorical effects of treatment, visit, treatment by visit interaction, and NAPLS risk score strata, and baseline use of antipsychotic medication, as well as the continuous fixed covariates of baseline score and baseline-by-visit interaction. The unstructured covariance structure will be used to model the within-patient errors. If this analysis fails to converge, compound symmetry covariance structure might be used. The Kenward-Roger approximation will be used to estimate the denominator degrees of freedom. Analyses will be implemented using █® PROC MIXED. The primary treatment comparisons will be between the placebo and BI 409306 with respect to the mean change from baseline. Adjusted mean change from baseline as well as treatment contrasts will be presented together with the 95% confidence intervals.

7.3.4 Safety analyses

Adverse events will be coded using the Medical Dictionary for Drug Regulatory Activities (MedDRA) coding dictionary. Standard BI summary tables and listings will be produced. All adverse events with an onset between start of treatment and end of the residual effect period (REP), a period of 7 days after the last dose of trial medication, will be assigned to the treatment period for evaluation.

All treated patients will be included in the safety analysis. In general, safety analyses will be descriptive in nature and will be based on BI standards. No hypothesis testing is planned.

Statistical analysis and reporting of adverse events will concentrate on treatment-emergent adverse events (i.e., by 'treatment at onset'). To this end, all adverse events occurring between start of treatment and end of the residual effect period will be considered 'treatment-emergent'. Adverse events that start before first drug intake and deteriorate under treatment will also be considered as 'treatment-emergent'.

Frequency, severity, and causal relationship of adverse events will be tabulated by system organ class and preferred term after coding according to the current version of the Medical Dictionary for Drug Regulatory Activities (MedDRA).

Laboratory data will be analysed both quantitatively as well as qualitatively. The latter will be done via comparison of laboratory data to their reference ranges. Values outside the reference range as well as values defined as clinically relevant will be highlighted in the listings. Treatment groups will be compared descriptively with regard to distribution parameters as well as with regard to frequency and percentage of patients with abnormal values or clinically relevant abnormal values.

Vital signs, physical examinations, or other safety-relevant data observed at screening, baseline, during the course of the trial and at the end-of-trial evaluation will be assessed with regard to possible changes compared to findings before start of treatment.

Descriptive statistics are planned to quantify the frequency of patients with suicidal ideation and behaviour as recorded on the C-SSRS at any post-baseline visit.

7.3.5 Pharmacokinetic and pharmacodynamic analyses

Pharmacogenetic analyses of gene variations within genes associated with the disease and NMDA-R signaling will be carried out using an explorative approach to test the potential influence on therapy response. Analyses may not be carried out if treatment response could not be shown.

7.4 INTERIM ANALYSES

Once there is a sufficient amount of data collected for review, the DMC will hold meetings three times per year. Analyses will be conducted to ensure there is no imbalance in safety endpoints. One formal unblinded interim analysis will be conducted by the DMC when approximately 67% of events have occurred to consider ending the trial early for overwhelming efficacy. Further details on alpha spending will be detailed in the DMC Charter and TSAP.

A blinded sample size reassessment interim analysis with the option to adjust the sample size will be performed by the Sponsor's Trial Statistician when 90% of patients have been randomised or at the same time as the formal interim analysis (whichever happens earlier). The number of observed remissions will be compared to the number predicted. If the actual number is lower than predicted (given the actual already documented study time of randomised patients at the scheduled post-baseline SOPS visits; prediction: 40% for placebo & 57% for BI 409306 at 52 weeks), the sample size may be increased to allow the trial to achieve full power up to a maximum sample size of 400 patients.

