5. VARIABLES AND THEIR ASSESSMENT

5.1 TRIAL ENDPOINTS

5.1.1 Primary Endpoint

The primary endpoint is time to remission from APS within a 52 week timeframe.

Per DSM-V, the proposed diagnostic criteria for APS are:

- A. At least one of the following of symptoms is present in attenuated form, with relatively intact reality testing and is of sufficient severity or frequency to warrant clinical attention:
 - Delusions
 - Hallucinations
 - Disorganized speech.
- B. Symptom(s) must have been present at least once per week in the last 1 month
- C. Symptom(s) must have begun or worsened in the past year
- D. Symptom(s) is sufficiently distressing and disabling to the individual to warrant clinical attention
- E. Symptom(s) is not better explained by another mental disorder, including: Depressive or bipolar disorder with psychotic features and is not attributable to physiological effects of a substance or another medical condition
- F. Criteria for any psychotic disorder have never been met.

A diagnosis of APS is defined by the presence of recent attenuated positive symptoms that meet ALL of 5 criteria: sufficient **severity** (criterion A), sufficient **frequency** (criterion B), **recency** of onset or worsening (criterion C), associated with sufficient distress or disability to warrant clinical attention (“**warrant attention** criterion,” criterion D), and not likely due to another disorder (“**attribution** criterion,” criterion E).

A patient in remission is defined as someone who no longer meets the severity criterion.

[figure not shown]
Remission from APS is defined as a score of <3 on all of the P1-P5 Positive Symptom items of the SOPS and maintained until the end of treatment.

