7.7 DETERMINATION OF SAMPLE SIZE

Remission rate of the population diagnosed with APS and without intervention was assumed to be 40% ([R16-0991](#)) by 52 weeks. The rate of remission for BI 409306 was assumed to be 57% by 52 weeks. This will lead to a hazard ratio of 1.652.

Other study considerations are:

- Two-sided alpha = 0.10
- Dropout = 20% after one year
- Interim analysis checking for early efficacy using user-defined alpha-spending boundary of 0.01 at the 67% information point

Table 7.7: 1 Power calculations for sample size (for both arms combined) of 300 for various remission rates for BI 409306 with fixed placebo group aggregate first remission rate prediction of 40% by 52 weeks

Remission Rate for Placebo	Remission Rate for BI 409306	Hazard Ratio	Risk Ratio	Power for N=300	# Events needed in total
40%	52%	1.437	1.300	64.9%	126
40%	55%	1.563	1.375	81.5%	130
40%	57%	1.652	1.425	89.3%	133
40%	59%	1.745	1.475	94.4%	136
40%	61%	1.843	1.525	97.4%	139

[Table 7.7: 1](#) displays the power achieved for 300 total randomized patients given a group aggregate first remission rate of 40% for placebo with two-sided $\alpha = 0.10$ and a user-defined

alpha spending boundary at interim analysis of $\alpha=0.01$ (two-sided). Group remission rates for BI 409306 treatment of 52%, 55%, 57%, 59% and 61% are considered. Total number of events needed to achieve the power reported is also shown.

Given remission rates of 40% for patients treated with placebo and 57% for patients treated with BI 409306, the risk ratio is 1.425 (implying that patients treated with BI 409306 will have 42.5% more chance of achieving remission of APS compared to placebo). A sample size of 300 (or 150 per group) was selected as the most logical for establishing proof of concept based on the risk / benefit considerations noted above. In addition this was the sample size used in the previous protocol and is kept the same. This translates to 89% power. The type I error was selected to be 10% since this is a phase II study meant to provide an understanding of the effectiveness of the drug without being too strict as in a confirmatory setting.

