One hundred and thirty three (133) events (remissions) are needed to be observed to meet the trial objectives. This will not be an event driven trial, so the trial will end when all randomised patients have reached 12 months exposure, regardless of number of remissions observed. However, a blinded sample size assessment will be performed (see [Section 7.4](#)) that may allow for an increase in sample size in an attempt to observe the number of remissions necessary for full power.

Calculations were performed using ADDPLAN® 6.1.1 statistical package by [REDACTED].

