6.6 HANDLING OF MISSING DATA AND OUTLIERS

Assessment of remission data (primary endpoint):

All patients will be followed up for remission from APS. As specified in [section 5.1](#), remission from APS has to be maintained until the end of treatment to satisfy the primary endpoint.

Any patient who has not remitted will be censored in the analysis of the primary endpoint at the time of their planned completion of 52-week treatment period or at the time of discontinuation.

Any patient who has remitted but relapsed to APS will be also censored in the analysis of primary endpoint at the time of their planned completion of 52-week treatment period or at the time of discontinuation.

Any patient who has an episode of psychosis will be censored at the time point of psychosis.

Patients who begin taking a new prescription or increase in dose of ongoing antipsychotics will not be considered eligible for remission. Such patients will be censored at the start of new prescription or increase of dose of ongoing antipsychotics.

No missing data will be imputed for primary and secondary analyses.

SCoRS:

For the SCoRS, if an individual item is missing, it should be imputed with the average of the patient's non-missing item scores.

PANSS positive symptoms (secondary analysis)

Change from baseline in PANSS positive symptoms will be evaluated using Mixed effect Model for Repeated Measures (MMRM) approach. This approach allows for missing data, assuming they are missing at random. All patients can be included in the model and missed visits will not be imputed. If a PANSS item is missing, the missing score on that individual PANSS item will not be imputed; if individual PANSS item is missing within a PANSS subscale, this subscale cannot be included in the calculation of the overall PANSS total score. Therefore, patients with missing individual PANSS items will also have a missing PANSS total score at that visit. However, subscale scores will be used for analysis if none of the individual items is missing.

AE dates

Missing or incomplete AE dates are imputed according to BI standards (see "Handling of missing and incomplete AE dates") [\(3\)](#).

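### Do the interim event count and the blinded re-sizing need their own rule for remissions that are ongoing or have already relapsed at the data cut?

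*Protocol*

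**What the plan says.** **Endpoint.** Protocol 5.1.1 and SAP 5.1 define remission as a score below 3 on all "of the P1-P5 Positive Symptom items of the SOPS and maintained until the end of treatment". For the primary analysis, SAP 6.6 adds: "Any patient who has remitted but relapsed to APS will be also censored in the analysis of primary endpoint". It also censors patients at psychosis or at a new or increased antipsychotic.

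**Interim decisions.** Protocol 7.4 contains two:

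- The efficacy look: "One formal unblinded interim analysis will be conducted by the DMC when approximately 67% of events have occurred".
- The blinded re-sizing, when 90% of patients are randomised or at the efficacy look, whichever is earlier: "The number of observed remissions will be compared to the number predicted". The condition for acting is "If the actual number is lower than predicted (given the actual already documented study time of randomised patients" at the scheduled SOPS visits, with 40% and 57% predicted at 52 weeks). The sample size may then rise to at most 400.

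**Planning rates.** Protocol 7.7 assumes 40% remission on placebo and 57% on BI 409306, which leads to 133 events. The title of Table 7.7:1 words the placebo figure as a "fixed placebo group aggregate first remission rate prediction of 40% by 52 weeks", and the explanatory text repeats it: "given a group aggregate first remission rate of 40% for placebo". The same section describes the review as one "that may allow for an increase in sample size in an attempt to observe the number of remissions necessary for full power".

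**The concern.** The endpoint is reversible, but both interim decisions use a running count. When 90% of patients are randomised, many are still on treatment. Some are in remission and may relapse; others have remitted and relapsed already. Section 7.4 does not say which of them are observed remissions or events, and the relapse rule in SAP 6.6 is written for the primary analysis.

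Three counts are conceivable:

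1. remission status at the last SOPS before the cut;
2. any first remission, whether or not it has since been lost;
3. only remissions already carried to the end of treatment.

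The word *first* in 7.7 gives the second some textual support. If the wrong count were used, the re-sizing could miss a real shortfall and leave the trial near 300, or it could signal a false one. The efficacy look could also rest on remissions that do not last.

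**Working it through.** **1. The plan's own figure.** Inputs from Protocol 7.7: 40% and 57% at 52 weeks, 20% dropout at one year, 150 per arm, two-sided alpha 0.10.

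- Yearly hazards: −ln(0.60) = 0.511; −ln(0.43) = 0.844; dropout −ln(0.80) = 0.223. Hazard ratio 0.844/0.511 = 1.652, as stated.
- Expected events per arm = 150 × a/(a+d) × [1 − exp(−(a+d))]. Placebo: 150 × 0.696 × 0.520 = 54.3. BI 409306: 150 × 0.791 × 0.656 = 77.8. Total 132.1, against 133 stated.
- Power = Φ(½√133 × ln 1.652 − 1.645) = Φ(1.25) = 89.4%, against 89.3% stated.
- The efficacy look falls at 0.67 × 133 ≈ 89 events.

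**2. Why the count matters if 40%/57% are first-remission rates.** Assume a constant relapse hazard r. The documents give none. The probability of being in remission at week 52 is a/(a+r) × [1 − exp(−(a+r))].

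| r per year (relapse within a year) | Maintained, placebo / drug | Events at N = 300 | Power at 300 | Power at 400 |
|---|---|---|---|---|
| 0.25 (22%) | 36% / 51% | 119 | 84% | 92% |
| 0.5 (39%) | 32% / 46% | 108 | 80% | 89% |
| 1.0 (63%) | 26% / 39% | 90 | 71% | 82% |

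Events allow for dropout. The hazard ratios used for power are 1.63, 1.61 and 1.59.

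**3. What each count would show at the re-sizing in those three cases.** These come from a simulated remission/relapse process observed at an assumed SOPS schedule, with two-year accrual.

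| r | Last-SOPS count / predicted | Trials flagged | First-remission count / predicted |
|---|---|---|---|
| 0.25 | 0.91 | 85% | 0.99 |
| 0.5 | 0.84 | 97% | 0.98 |
| 1.0 | 0.72 | 100% | 0.96 |

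Status at the last SOPS sees the shortfall; the first-remission count barely does. A separate simulation used 24-month accrual and the assumed rule N = 300 × predicted/observed, kept between 300 and 400. At r = 0.3/0.7/1.5 it gave average N of 337/374/399 by last SOPS against 313/316/322 by first remission. Power was 86.8/82.5/75.6% against 83.8/74.9/67.3%. Over accrual of 18 to 36 months the gain was 2.5 to 9.7 points.

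**4. If 40%/57% are maintained rates.** Both counts leave N at 300 to 306. The last-SOPS count is 1.06 to 1.11 times the prediction at 39% to 63% yearly relapse. The first-remission count is 1.23 to 1.44 times.

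**5. Which count the plan implies.**

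- *First remissions regardless of relapse* is excluded by 5.1.1 and SAP 6.6: a relapsed patient is not a remission for this trial. It also fails the purpose in 7.7, since the remissions needed for full power are those the final analysis counts. The main assumptions in 7.7, its closing paragraph and the prediction in 7.4 all give 40% and 57% without *first*.
- *Completed remissions only* gives about 33 to 61 against 74 to 87 predicted (r up to 0.5). That shortfall is false because the two sides cover different patients. Section 7.4 avoids it by predicting from the documented SOPS time of all randomised patients, so the observed side must use the same patients and time.
- *Status at the last SOPS* is what remains. It applies the final rule to the data available at the cut.

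**6. The efficacy look under that count.** Of about 90 provisional events, 77 to 85 remain events at the end, so 5% to 14% reverse. One-sided type I error stayed at or below 5% in the null runs. For r up to 1 per year, at most 0.7% of trials stopped when the final analysis would have failed.

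**The case for a change.** The strongest case is that a decision worth up to 100 patients, and a possible efficacy stop, should not depend on inference. The word *first* appears twice in 7.7, and Protocol 7.3.1 dates remission at the visit where the criteria are met. A statistician comparing like with like could count first remissions. For a drug that brings faster but transient remission, with equal week-52 rates, the first-remission count crossed the interim boundary in 71% of simulated trials, against 2.4% by last-SOPS status. Section 7.4 defers only alpha spending to the DMC charter and SAP, and the sponsor's statistician does the re-sizing, so the charter may not cover it.

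What stands: the text is silent, the counts differ, and the last-SOPS count is only an approximation. At 86% yearly relapse it overcounts by 22%. It then detects a true fall to 32%/47% in 65% of trials, against 90% if only patients who reached the end of treatment are compared with their own prediction. An early stop would also leave some ongoing remissions unconfirmed.

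What does not stand is the step from silence to harm. The re-sizing loss needs 7.7 to mean first-remission rates and the statistician to count patients whom the endpoint excludes. The larger losses also need substantial relapse and a mechanical formula, whereas 7.4 says only that the size may be increased. The DMC charter was not available, parts of the SAP are redacted, and its history table lists an initial December 2017 version for trial conduct. A written rule may therefore exist.

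**Conclusion.** No change to the plan follows. Protocol 7.4 omits an operational detail, but the maintained-remission endpoint, the relapse rule in SAP 6.6 and the time-scaled prediction in 7.4 together lead a competent statistician to remission status at the last SOPS. That count tracks the final events adequately at low to moderate relapse: 6% to 11% above prediction at 39% to 63% a year, worsening beyond that. The word *first* in 7.7 is best read as loose labelling.

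The power difference of 2.5 to 9.7 points applies only if 40%/57% are first-remission rates and relapsed patients are counted. It depends on assumed relapse, accrual and re-sizing rules that the documents do not give. If 40%/57% are maintained rates, the re-sizing is essentially the same under both counts. SAP section 4 also reports a much smaller trial than intended because of recruitment, which leaves little practical role for an upward adjustment, although the judgement here is on the plan as written.

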7.5 HANDLING OF MISSING DATA

All patients who have not achieved remission will be censored in the analysis of the primary endpoint at the time of last known SOPS assessment. No missing data will be imputed for

the primary and secondary analyses. For secondary endpoints, the statistical model using MMRM will handle missing data based on a likelihood method under the “missing at random” assumption. All FAS patients can be included in the model and therefore participate in variance estimation.

For the SCoRS, if an individual item is missing, it should be imputed with the average of the patient’s non-missing item scores. If >5 responses of the 20 items are missing, the composite score of SCoRS will be missing.

Further details about handling missing data will be specified in the TSAP.

7.6 RANDOMISATION

Patients will be randomised in blocks to double-blind treatment. Approximately equal numbers of patients will be randomised to each treatment group. The randomisation will be stratified by baseline use of antipsychotic medication. BI will arrange for the randomisation and the packaging and labelling of trial medication. The randomisation list will be generated using a validated system, which involves a pseudo-random number generator so that the resulting treatment will be both reproducible and non-predictable. The block size will be documented in the CTR. Access to the codes will be controlled and documented.

7.7 DETERMINATION OF SAMPLE SIZE

Remission rate of the population diagnosed with APS and without intervention was assumed to be 40% ([R16-0991](#)) by 52 weeks. The rate of remission for BI 409306 was assumed to be 57% by 52 weeks. This will lead to a hazard ratio of 1.652.

Other study considerations are:

- Two-sided alpha = 0.10
- Dropout = 20% after one year
- Interim analysis checking for early efficacy using user-defined alpha-spending boundary of 0.01 at the 67% information point

Table 7.7: 1 Power calculations for sample size (for both arms combined) of 300 for various remission rates for BI 409306 with fixed placebo group aggregate first remission rate prediction of 40% by 52 weeks

Remission Rate for Placebo	Remission Rate for BI 409306	Hazard Ratio	Risk Ratio	Power for N=300	# Events needed in total
40%	52%	1.437	1.300	64.9%	126
40%	55%	1.563	1.375	81.5%	130
40%	57%	1.652	1.425	89.3%	133
40%	59%	1.745	1.475	94.4%	136
40%	61%	1.843	1.525	97.4%	139

[Table 7.7: 1](#) displays the power achieved for 300 total randomized patients given a group aggregate first remission rate of 40% for placebo with two-sided $\alpha = 0.10$ and a user-defined

alpha spending boundary at interim analysis of $\alpha=0.01$ (two-sided). Group remission rates for BI 409306 treatment of 52%, 55%, 57%, 59% and 61% are considered. Total number of events needed to achieve the power reported is also shown.

Given remission rates of 40% for patients treated with placebo and 57% for patients treated with BI 409306, the risk ratio is 1.425 (implying that patients treated with BI 409306 will have 42.5% more chance of achieving remission of APS compared to placebo). A sample size of 300 (or 150 per group) was selected as the most logical for establishing proof of concept based on the risk / benefit considerations noted above. In addition this was the sample size used in the previous protocol and is kept the same. This translates to 89% power. The type I error was selected to be 10% since this is a phase II study meant to provide an understanding of the effectiveness of the drug without being too strict as in a confirmatory setting.

One hundred and thirty three (133) events (remissions) are needed to be observed to meet the trial objectives. This will not be an event driven trial, so the trial will end when all randomised patients have reached 12 months exposure, regardless of number of remissions observed. However, a blinded sample size assessment will be performed (see [Section 7.4](#)) that may allow for an increase in sample size in an attempt to observe the number of remissions necessary for full power.

Calculations were performed using ADDPLAN® 6.1.1 statistical package by [REDACTED].

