7.2 NULL AND ALTERNATIVE HYPOTHESES

The hypotheses for the superiority testing of the primary endpoint are (HR = hazard ratio):

$$H_0: HR_{BI\ 409306\ / placebo} = 1 \quad \text{vs.} \quad H_a: HR_{BI\ 409306\ / placebo} \neq 1$$

Superiority will be declared if the hazard ratio between BI 409306 vs. placebo is significantly greater than 1 at the two-sided type I error level $\alpha = 0.10$.

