7.3.1 Primary endpoint analyses

The primary endpoint is the time to remission from APS as defined in [Section 5.1.1](#).

The equality of the hazard rates will be tested by the Wald test for the treatment effect in a stratified Cox proportional hazards model at the two-sided 10% significance level. The model includes the treatment effect and NAPLS risk score as covariates and is stratified by baseline use of antipsychotic medication. Breslow's method for handling ties will be used.

The same stratified Cox proportional hazards model will be used to estimate the hazard ratio of BI 409306 vs. placebo and the asymptotic 90% Wald confidence interval. A hazard ratio of more than one favors BI 409306. The analysis will be implemented using █® PROC PHREG. Cox proportional hazard model assumptions will be verified.

[figure not shown]
The primary analysis will be performed on the FAS for the on treatment period. The date of remission will be the visit date on which the patient taking the assessment meets the remission criteria. The time to remission is defined to be the start of treatment until remission is achieved. Although patients who discontinue study medication will be followed until the end of the trial for the primary endpoint, the data collected after treatment discontinuation will only be used for a sensitivity analysis. Patients who are lost-to-follow up will be censored for the primary endpoint at the time of their last known SOPS assessment. Patients who begin taking a new prescription or increase in dose of ongoing antipsychotics will be considered as not eligible for remission. Such patients will be censored at the start of new prescription or increase of dose of ongoing antipsychotics. Further details regarding these analyses will be included in the TSAP.

The following sensitivity analyses will be performed: (1) on the primary endpoint that includes only patients from the TS during the time of the full follow-up period and (2) excluding patients who were recruited from the enriched population prior to amendment 3.

Subgroup analyses are planned and will be pre-specified in the TSAP.

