3. INTRODUCTION

As per ICH E9, the purpose of this document is to provide a more technical and detailed elaboration of the principal features of the analysis described in the protocol, and to include detailed procedures for executing the statistical analysis of the primary and secondary variables and other data.

This TSAP assumes familiarity with the Clinical Trial Protocol (CTP), including Protocol Amendments. In particular, the TSAP is based on the planned analysis specification as written in CTP Section 7 “Statistical Methods and Determination of Sample Size”. Therefore, TSAP readers may consult the CTP for more background information on the study, e.g., on study objectives, study design and population, treatments, definition of measurements and variables, planning of sample size, randomization.

SAS® Version 9.4 or higher will be used for all analyses.

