4. CHANGES IN THE PLANNED ANALYSIS OF THE STUDY

Due to recruitment challenges, the trial has a much smaller sample size than originally intended. The following are the changes in the analyses due to the limited sample size:

- No subgroup analyses.
- No evaluation of psychometric properties of SIPS/SOPS.
- No additional sensitivity analyses excluding patients who were recruited from the enriched population prior to amendment 3.

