7.4 PRIMARY ENDPOINT(S)

The hypothesis testing strategy for primary endpoint is described in **Section 7.2 of the CTP:**

The hypothesis for the superiority testing of the primary endpoint time to remission from APS is (HR = hazard ratio):

$H_0: HR_{BI\ 409306\ / placebo} = 1$ vs. $H_a: HR_{BI\ 409306\ / placebo} \neq 1$, where $HR_{BI\ 409306}$ is the hazard ratio for the active treatment arms (i.e. BI 409306 50 mg q.d.), over 52 weeks.

Superiority will be declared if the hazard ratio between BI 409306 vs. placebo is statistically significantly less than 1 at the two-sided type I error level $\alpha = 0.1$.

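### The final SAP says the trial is much smaller than planned, but its visible text does not replace the protocol's 133 remissions and 89% power, which hold only for about 300 patients

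*Protocol*

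**What the plan says.** **Size and power.** Protocol 7.7 assumes 40% remission on placebo and 57% on BI 409306 by 52 weeks (hazard ratio 1.652), two-sided alpha 0.10, 20% dropout at one year, and one interim look spending 0.01 at 67% information. For 300 patients it concludes: "This translates to 89% power". It adds that 133 "events (remissions) are needed to be observed to meet the trial objectives". All five rows of Table 7.7:1 (64.9% to 97.4% power) are for 300 patients. Protocol 7.4 foresees a change in size in one direction only, an increase to at most 400.

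**The change.** SAP section 4 states: "Due to recruitment challenges, the trial has a much smaller sample size than originally intended". It lists three analyses dropped for that reason: subgroups, the psychometric evaluation of SIPS/SOPS, and the sensitivity analysis excluding patients recruited before amendment 3. It gives no number. SAP section 3 names the topics for which readers may consult the protocol, among them "definition of measurements and variables, planning of sample size, randomization".

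**The test.** SAP 7.4 keeps a superiority test at two-sided 0.1, but declares success if the "hazard ratio between BI 409306 vs. placebo is statistically significantly less than 1 at the two-sided type I error level" 0.1. Protocol 7.2 declares it if the "hazard ratio between BI 409306 vs. placebo is significantly greater than 1 at the two-sided type I error level" 0.10, and protocol 7.3.1 explains: "A hazard ratio of more than one favors BI 409306". Protocol 7.3.1 also plans the estimate; the same Cox model is "used to estimate the hazard ratio of BI 409306 vs. placebo and the asymptotic 90% Wald confidence interval".

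**The concern.** The SAP treats the shortfall as serious enough to remove secondary work, yet does not say what it does to the primary test. The only planning figures a reader can find belong to a trial of 300 or more. A non-significant result could then be set against 89% power and read as evidence of no effect, when on the plan's own assumptions the test might have had little better than an even chance of detecting the planned effect, or less.

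The success rule in SAP 7.4 bears on the same text. The endpoint is time to remission, so a hazard ratio below 1 means slower remission on BI 409306. Taken literally, the SAP rule would reward the wrong result, and a detectable hazard ratio cannot be stated clearly until the direction is settled.

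**Working it through.** **Inputs (protocol 7.7).** Remission 40% and 57% at one year; dropout 20% at one year; 1:1 allocation; two-sided alpha 0.10 (critical value 1.645).

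**Model.** Constant hazards over one year:

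- placebo: −ln(0.60) = 0.5108
- BI 409306: −ln(0.43) = 0.8440
- dropout: −ln(0.80) = 0.2231
- hazard ratio: 0.8440 / 0.5108 = 1.652, as stated; its log is 0.502

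The chance of an observed remission in an arm with hazard λ and dropout hazard δ is λ/(λ+δ) × [1 − exp(−(λ+δ))]. This gives 0.3619 on placebo and 0.5188 on BI 409306. Expected events = (N/2) × (0.3619 + 0.5188). Power = Φ(√(events/4) × ln HR − 1.645).

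**Step 1: the plan's own figures.** At N = 300, expected events are 150 × 0.8807 = 132.1 (133 stated). Then √(132.1/4) × 0.502 = 2.885, and Φ(2.885 − 1.645) = 89.3%, as in Table 7.7:1. The other rows also reproduce: 64.9%, 81.5%, 94.4% and 97.4%. With the 0.01 interim spend the final critical value is 1.651 and power is 89.2%, so the interim look hardly matters. Protocol 7.7 contains no arithmetic error.

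**Step 2: smaller totals.** The documents do not give the achieved N, so the totals below are assumed. The planning effect is held fixed.

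| N (assumed) | Expected remissions | Share of 133 | Power at HR 1.652 | HR detectable with 80% power (remission on BI 409306) | Expected 90% CI at HR 1.652 |
|---|---|---|---|---|---|
| 300 | 132 | 99% | 89% | 1.55 (55%) | 1.24 to 2.20 |
| 200 | 88 | 66% | 76% | 1.69 (58%) | 1.16 to 2.35 |
| 150 | 66 | 50% | 65% | 1.82 (61%) | 1.10 to 2.48 |
| 100 | 44 | 33% | 51% | 2.05 (65%) | 1.01 to 2.71 |
| 50 | 22 | 17% | 32% | 2.65 (74%) | 0.82 to 3.33 |

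The interval is 1.652 × exp(±1.645 × 2/√events). The detectable hazard ratio holds placebo at 40% and lets events rise with the effect. If events are instead scaled as 133 × N/300, the values at N = 100 and 50 are 2.11 and 2.88, so this column is approximate at small N.

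**Step 3: thresholds.** For 80% power at HR 1.652, events = 4 × (1.645 + 0.842)² / 0.502² ≈ 98, which needs N of about 223. Power is 49.8% at N = 97 and 50.2% at N = 98. Expecting 133 remissions takes 133 / (132.1/300) ≈ 302 patients.

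**Step 4: direction of the success rule.** Protocol 7.2 and 7.3.1 agree with each other and with the endpoint: above 1 favours BI 409306. SAP 7.4 cites protocol 7.2 as its source and states the opposite. The amendment 3 description in protocol section 11 shows that the protocol's rule was reversed when the primary endpoint changed from first psychosis to remission. The SAP wording matches the superseded direction.

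**The case against.** The strongest reply is that nothing is hidden or misapplied. SAP section 4 says openly that the sample is much smaller, Table 7.7:1 is labelled for 300 patients, and the SAP nowhere claims 89% for the reduced trial. The trial is not event driven, so no test, alpha level or stopping point depends on restating power. The planned 90% interval will show the precision reached, and this is a phase II proof of concept. All of that stands. It makes the point one of reporting and interpretation, not of validity, but it does not supply the missing figures.

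Parts of the public SAP are blacked out, so only the visible text can be judged. Section 4, where the change is declared, is readable and carries no number.

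Three stronger readings are tempting, and the documents do not support them:

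- *That 89% was miscalculated.* It reproduces for 300 patients.
- *That the trial has some particular low power.* The achieved N is not given; the table in the working is a range, not a finding.
- *That power was overstated because the 40% is a first-remission rate.* The title of Table 7.7:1 and the text beneath it use that term, and protocol 5.1.1 requires remission maintained to the end of treatment. But 7.7 opens with a plain remission rate, and the wording may mean only time to first event. If treatment also helped patients stay in remission, the hazard ratio for sustained remission could exceed 1.652. This is an ambiguity to clear up, not a shown error.

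It is also fair to say that the SAP 7.4 contradiction is not a sample-size matter. It changes no power figure here and has to be fixed on its own merits.

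**Conclusion.** The point holds as an omission in the final SAP. The 300 patients, 133 remissions and 89% power are internally correct, but they no longer describe the trial being analysed, and the visible text puts nothing in their place. On the planning assumptions (constant hazards, 40% against 57%, 20% dropout, equal allocation), halving the trial would take power from 89% to about 65%, and a third of the planned size would leave about 51%. Confidence is high that the figures are missing; the size of the loss cannot be fixed from the documents. The change should be made, although the primary analysis can be run without it. Separately, the success rule in SAP 7.4 directly contradicts protocol 7.2 and 7.3.1 and needs correcting whatever the sample size.

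**What to change.** 1. Add to SAP section 4 the achieved number randomised, the expected number of remissions, the power at hazard ratio 1.652, and the detectable hazard ratio or expected 90% interval width. Compute all of them at the planning effect, not the observed one, so that this does not become post-hoc power. These lines are an addition: 89% and 133 stand in protocol 7.7, not in the SAP.
2. State there that the protocol's 89% and 133 no longer apply, and that the result will be read through the hazard ratio and 90% interval already planned in protocol 7.3.1.
3. Correct SAP 7.4 so that superiority requires a hazard ratio above 1, in line with protocol 7.2 and 7.3.1.
4. In one line, say whether the assumed 40% is a first or a sustained remission rate.

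The cost is a few lines of text and a short recalculation, with no extra patients, data or analyses. The downside is a less favourable stated power.
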